## 9.4 Treatments

### 9.4.1 Treatments Administered

#### 9.4.1.1 Test Drug: Lenvatinib

Lenvatinib capsules will be administered orally, QD in continuous 28-day cycles. The starting dose of lenvatinib will be based on the subject's baseline BW as follows:

- BW  $\geq$ 60 kg — Lenvatinib 12 mg (taken as three 4-mg capsules) QD.
- BW  $<$ 60 kg — Lenvatinib 8 mg (taken as two 4-mg capsules) QD.

Study medication should be taken at approximately the same time each day in a fasting state or following a meal.

If a dose is missed and cannot be taken within 12 hours, then that dose should be skipped and the next dose should be taken at the usual time of administration.

Lenvatinib treatment will continue until disease progression, development of unacceptable toxicity, subject requests to discontinue, withdrawal of consent, or termination of the study

by the sponsor. The duration of lenvatinib treatment for each subject is estimated to be 6 to 8 months.

If holidays or personal schedules make administration impossible on the scheduled days, then administration should be resumed as soon as possible.

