**Table 1 Dose Modification and Treatment Discontinuation Guidelines for Management of Lenvatinib-Related Toxicity**

Study Treatment Dose Reduction and Interruption Instructions		
Non-Hematologic Toxicities		
Treatment-Related Toxicitya,b	Management	Dose Adjustment
Grade 1 or Tolerable Grade 2		
	Continue treatment	No change
Intolerable Grade 2c,d or Grade 3e,d		
First occurrence	Interrupt until resolved to Grade 0-1 or baseline	One-level reduction
Second occurrence (same toxicity or new toxicity)	Interrupt until resolved to Grade 0-1 or baseline	One-level reduction
Third occurrence f (same toxicity or new toxicity)	Interrupt until resolved to Grade 0-1 or baseline	One-level reduction
Fourth occurrence (same toxicity or new toxicity)	Interrupt until resolved to Grade 0-1 or baseline	Discuss with sponsor
Grade 4g: Discontinue Study Treatment		
Hematologic Toxicities and Proteinuria		
Treatment-Related Toxicitya	Management	Dose Adjustment
Grade 1 or Grade 2		
	Continue treatment	No change
Grade 3		
First occurrence	Interrupt until resolved to Grade 0-2 or baseline	No change
Second occurrence (same toxicity or new toxicity)	Interrupt until resolved to Grade 0-2 or baseline	One-level reduction
Third occurrence (same toxicity or new toxicity)	Interrupt until resolved to Grade 0-2 or baseline	One-level reduction
Fourth occurrence f (same toxicity or new toxicity)	Interrupt until resolved to Grade 0-2 or baseline	One-level reduction
Fifth occurrence (same toxicity or new toxicity)	Interrupt until resolved to Grade 0-2 or baseline	Discuss with sponsor
Grade 4		
First occurrence	Interrupt until resolved to Grade 0-2 or baseline	One-level reduction
Second occurrence (same toxicity or new toxicity)	Interrupt until resolved to Grade 0-2 or baseline	One-level reduction

Third occurrence f (same toxicity or new toxicity)	Interrupt until resolved to Grade 0-2 or baseline	One-level reduction
Fourth occurrence (same toxicity or new toxicity)	Interrupt until resolved to Grade 0-2 or baseline	Discuss with sponsor

Note: Grading according to Common Terminology Criteria for Adverse Events (CTCAE) v4.03.

AEs = adverse events, ALT = alanine aminotransferase, AST = aspartate aminotransferase, ULN = upper limit of normal

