antihypertensive should be added. For subjects with hypertension and proteinuria, treatment with an angiotensin-converting enzyme inhibitor or angiotensin-II receptor antagonist is preferred.

**Study drug should be withheld in any instances where a subject is at imminent risk to develop a hypertensive crisis or has significant risk factors for severe complications of uncontrolled hypertension (eg, BP  $\geq$ 160/100 mmHg, significant risk factors for cardiac disease, intracerebral hemorrhage, or other significant comorbidities). Once the subject has been on same hypertensive medications for at least 48 hours and the BP is controlled, study drug should be resumed as described below.**

Subjects with systolic BP  $\geq$ 160 mmHg or diastolic BP  $\geq$ 100 mmHg must have their BP monitored every 2 weeks (on Day 15 or more frequently as clinically indicated) until systolic BP has been  $\leq$ 150 mmHg and diastolic BP has been  $\leq$ 95 mmHg for 2 consecutive treatment cycles. If a new event of systolic BP  $\geq$ 160 mmHg or diastolic BP  $\geq$ 100 mmHg occurs, the subject must resume the Day 15 evaluation until systolic BP has been  $\leq$ 150 mmHg and diastolic BP has been  $\leq$ 95 mmHg for 2 consecutive treatment cycles.

The following guidelines should be followed for the management of systolic BP  $\geq$ 160 mmHg or diastolic BP  $\geq$ 100 mmHg confirmed on repeat measurements after 30 minutes:

- Continue study drug and institute antihypertensive therapy for subjects not already receiving antihypertensive medication.
- For those subjects already on antihypertensive medication, the dose of the current agent may be increased, if appropriate, or one or more agents of a different class of antihypertensive should be added.
- If systolic BP  $\geq$ 160 mmHg or diastolic BP  $\geq$ 100 mmHg persists despite maximal antihypertensive therapy, then study drug administration should be interrupted and restarted at a dose of 8 mg QD (one dose level reduction as specified in table above) only when systolic BP  $\leq$ 150 mmHg and diastolic BP  $\leq$ 95 mmHg and the subject has been on a stable dose of antihypertensive medication for at least 48 hours.

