  - If systolic BP  $\geq$ 160 mmHg or diastolic BP  $\geq$ 100 mmHg recurs on the 8 mg QD dose despite optimal management of hypertension with antihypertensive medications (either by dose increase or the addition of a different class of antihypertensive), then study drug administration should be interrupted and restarted at a dose of 4 mg QD (one dose level reduction as specified in the table above) only when systolic BP  $\leq$ 150 mmHg and diastolic BP  $\leq$ 95 mmHg and the subject has been on a stable dose of antihypertensive medication for at least 48 hours.
  - If systolic BP  $\geq$ 160 mmHg or diastolic BP  $\geq$ 100 mmHg recurs on the 4 mg QD dose despite optimal management of hypertension with antihypertensive medications (either by dose increase or the addition of a different class of antihypertensive), then study drug administration should be interrupted and a restart of study medication should be discussed with the sponsor.

The following guidelines should be followed for the management of Grade 4 hypertension (life-threatening consequences):

- Institute appropriate medical management
- Discontinue study drug.

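### The hypertension rule's fixed 8 mg QD restart is a one-level reduction only for subjects on 12 mg QD; for a subject already on 8 mg QD the number gives no reduction, while its own label gives 4 mg QD

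*Combined protocol and SAP*

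**What the plan says.** **Starting dose.** Section 9.4.1.1 sets it by baseline body weight: 12 mg QD at 60 kg or more, and "Lenvatinib 8 mg (taken as two 4-mg capsules) QD" below 60 kg.

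**Hypertension rule.** Section 9.4.1.1.2, repeated in the synopsis under Management of Hypertension, has three steps for systolic pressure of at least 160 mmHg or diastolic of at least 100 mmHg:

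- Step 1: if it "persists despite maximal antihypertensive therapy", study drug is "interrupted and restarted at a dose of 8 mg QD (one dose level reduction as specified in table above"). Restart requires a pressure no higher than 150/95 mmHg and that "the subject has been on a stable dose of antihypertensive medication for at least 48 hours".
- Step 2: if it "recurs on the 8 mg QD dose despite optimal management of hypertension with antihypertensive medications", drug is interrupted and restarted at 4 mg QD, again described as one level down.
- Step 3: if it "recurs on the 4 mg QD dose despite optimal management of hypertension with antihypertensive medications", drug is interrupted and "a restart of study medication should be discussed with the sponsor".

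**Table 1.** For the first occurrence of an intolerable Grade 2 or a Grade 3 non-hematologic toxicity, the instruction is "Interrupt until resolved to Grade 0-1 or baseline", followed by a one-level reduction. Footnote f tells sites to skip only the third-occurrence step for subjects who started at 8 mg.

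**Dose ladder.** The synopsis dose-reduction instructions take each reduction from the preceding level. For subjects of 60 kg or more they list 12, 8 and 4 mg daily, then 4 mg every other day. A reduced dose may not be raised again.

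**The concern.** Step 1 gives a number and a description of that number, and the two agree for only one current dose. A subject whose first persistent episode occurs on 8 mg QD meets the step 1 trigger as written. A site that follows the number returns this subject to the dose at which blood pressure could not be controlled. A site that follows the parenthesis, or the table it points to, restarts at 4 mg QD.

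Two things are at stake. The first is safety: the literal reading delays the first reduction under this rule from the first episode to the second. The second is reporting: section 9.7.1.8.1 summarises dose reductions, relative dose intensity and the share of subjects completing 2, 4 and 6 lenvatinib cycles without a reduction for an adverse event. Those summaries could mix two dosing rules.

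**Working it through.** **Step 1 against the ladder.** Inputs: the ladder from the synopsis and the 8 mg restart dose from section 9.4.1.1.2. Change = restart dose minus current dose.

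| Current dose | One level down | Step 1 number | Change | Label correct? |
|---|---|---|---|---|
| 12 mg QD | 8 mg QD | 8 mg QD | 8 − 12 = −4 mg (−33%) | Yes |
| 8 mg QD | 4 mg QD | 8 mg QD | 8 − 8 = 0 mg | No |

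The plan's figure reproduces for 12 mg subjects only.

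**Which reading does the table support?** A 12 mg starter has three levels below the start (8 mg, 4 mg, 4 mg every other day). That matches three one-level reductions in Table 1 before sponsor discussion at the fourth occurrence. An 8 mg starter has two levels below the start, and footnote f accordingly removes one step, the third. The first-occurrence step stays, so an 8 mg starter goes from 8 to 4 mg at the first event. The table was adapted for 8 mg starters; the hypertension rule was not.

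**Does step 2 cover the case?** Step 2 does lead from 8 to 4 mg, but it sits under step 1 and is worded for pressure that recurs on 8 mg. A first episode that persists on 8 mg fits the step 1 wording more directly. Step 2 does not clearly settle it.

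**Size for one subject.** Restart dose after a first persistent episode on 8 mg:

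- By the number: 8 mg. By the label: 4 mg. Difference: 4/8 = 50%.
- As a share of the starting dose, for an 8 mg starter: 8/8 = 100% against 4/8 = 50%.
- For a 12 mg starter already on 8 mg: 8/12 = 67% against 4/12 = 33%.
- Episodes needed before the first reduction under this rule: 2 by the number, 1 by the label.

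**Illustration for dose intensity (assumed timing).** Take an 8 mg starter with the episode at the end of cycle 2, followed for 6 cycles, ignoring the interruption:

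- Number, no recurrence: (2×8 + 4×8)/(6×8) = 48/48 = 100%.
- Label: (2×8 + 4×4)/(6×8) = 32/48 = 67%.
- Number, with a recurrence at the end of cycle 4 that triggers step 2: (4×8 + 2×4)/(6×8) = 40/48 = 83%.

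**Reach.** The completion-without-reduction percentages can move only through 8 mg starters, because a 12 mg starter already lowered to 8 mg for an adverse event already counts as reduced. Table 4 has no lenvatinib dose term. Its half-widths reproduce from 1.96 × √(0.75 × 0.25/n): 8.5% at n = 100 and 12.0% at n = 50.

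**The case against.** The best defence is that the protocol largely answers the question itself. The parenthesis sends the reader to the dose table, which gives a one-level reduction at first occurrence. The synopsis takes reductions from the preceding level, and its example is explicitly for subjects of 60 kg or more. Step 2 identifies 4 mg as one level below 8 mg. On this view the 8 mg figure is simply the 12 mg starter's case, and a site would have to overlook all of that to restart an 8 mg subject at 8 mg. This carries weight: it shows which reading is intended and makes widespread misapplication unlikely. It does not remove the contradiction, because the only explicit dose in step 1 is 8 mg, with no condition attached.

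Some already-reduced subjects do fall under step 2. A 12 mg starter who had pressure at this level earlier, had it controlled, was lowered to 8 mg for another toxicity and then had it again fits the recurrence wording and goes to 4 mg. Not every such subject is affected.

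Three stronger readings are tempting, and the documents do not support them:

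- *That step 1 raises a subject on 4 mg QD to 8 mg.* The label calls the step a reduction, and the synopsis forbids raising a reduced dose.
- *That a first persistent episode on 4 mg QD has no instruction at all.* Step 3 is worded for recurrence, but Table 1 and the ladder arguably give 4 mg every other day.
- *That a definite number of subjects is affected.* This would need the share under 60 kg, the share of 12 mg starters already at 8 mg and the share with pressure uncontrolled on maximal treatment. The documents give none of them.

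**Conclusion.** The inconsistency is real and narrow. Step 1 is correct for subjects on 12 mg QD. For a first persistent episode on 8 mg QD, its number gives no reduction, while its label, the ladder and Table 1 give 4 mg QD: a 4 mg/day difference, and one extra episode before the first reduction.

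Practical harm is limited on either reading. Drug is interrupted, restart needs controlled pressure and 48 hours on stable antihypertensives, a recurrence on 8 mg leads to 4 mg, and Grade 4 hypertension leads to discontinuation. The dose-intensity figures above illustrate one subject under assumed timing and do not estimate an effect on the trial.

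The consequence stays within Treatment Period 1 dosing safety and descriptive exposure reporting. A reader might infer that the trial's conclusions are at risk. They are not: the primary endpoint concerns adverse events on the subsequent treatment, and neither the definitions and planned analyses of the secondary endpoints nor the sample size depend on this rule. It merits correction because a dosing instruction for uncontrolled hypertension should give one answer per subject.

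**What to change.** In the synopsis (Management of Hypertension) and in section 9.4.1.1.2, replace the fixed restart doses in steps 1 and 2 with: *interrupt study drug and restart at one dose level below the current dose (12 mg QD to 8 mg QD; 8 mg QD to 4 mg QD)*. Keep the existing blood-pressure and 48-hour conditions for restart.

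The sponsor-discussion step at 4 mg QD can stay as it is. Extending it to a first episode at 4 mg is an optional clarification. If it is added, the amendment should say that it takes precedence over the Table 1 route to 4 mg every other day.

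The cost is a wording change in two places. Dosing of 12 mg subjects, data collection, sample size and the primary analysis do not change.

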#### 9.4.1.1.3 MANAGEMENT OF PROTEINURIA

Regular assessment for proteinuria should be conducted as detailed in the Schedule of Procedures/Assessments. Guidelines for assessment and management of proteinuria are summarized as follows:

##### Grading of Proteinuria

- Grading of proteinuria according to CTCAE v4.03 will be based on the 24-hour urinary protein result. Management of lenvatinib administration will be based on the grade of proteinuria according to the Dose Modification Guidelines ([Table 1](#)).

##### Detection and Confirmation

1. Perform urine dipstick testing per the Schedule of Assessments
2. A 24-hour urine collection (initiated as soon as possible and at least within 72 hours) or an immediate spot urine protein-to-creatinine ratio (UPCR) test is required in the following situations:
  - a. The first (initial) occurrence of  $\geq 2+$  proteinuria on urine dipstick while on study drug
  - b. A subsequent increase in severity of urine dipstick proteinuria occurring on the same lenvatinib dose level
  - c. When there has been a lenvatinib dose reduction and at the new dose level the urine protein dipstick result is  $\geq 2+$
3. A 24-hour urine collection (initiated as soon as possible and at least within 72 hours) to verify the grade of proteinuria is required when UPCR is  $\geq 2.4$ .

##### Monitoring

- Urine dipstick testing for subjects with proteinuria  $\geq 2+$  should be performed every 2 weeks (or more frequently as clinically indicated) until the results have been 1+ or negative for 2 consecutive treatment cycles.

#### 9.4.1.1.4 MANAGEMENT OF HEPATOTOXICITY

Regular monitoring of liver function tests (eg, ALT, AST, bilirubin levels) should be conducted as detailed in the Schedule of Assessments/Procedures ([Table 3](#)) and as clinically indicated. Worsening liver function including hepatic encephalopathy should be closely monitored. If signs occur indicating a decrease in liver function by 1 grade or more from baseline, the instructions contained in [Table 1](#) should be followed. Appropriate supportive care should be provided together with close monitoring. If hepatic failure occurs, lenvatinib must be discontinued.

#### 9.4.1.1.5 MANAGEMENT OF THROMBOEMBOLIC EVENTS

Subjects should be advised to pay attention to the symptoms suggestive of venous thromboembolic events, which include acute onset of dyspnea, chest pain, cough, hemoptysis, tachypnea, tachycardia, cyanosis, deep vein thrombosis signs including lower-extremity swelling, redness and warmth to touch or tenderness. In case any of these signs or symptoms appear, subjects should be instructed to report such signs and symptoms promptly to the treating physician. If a thromboembolic event is confirmed, instructions contained in [Table 1](#) should be followed. Appropriate supportive care should be provided together with close monitoring. If a subject experiences life-threatening (Grade 4) thromboembolic reactions, including pulmonary embolism, lenvatinib must be discontinued.

#### 9.4.1.1.6 MANAGEMENT OF POSTERIOR REVERSIBLE ENCEPHALOPATHY SYNDROME (PRES)

In clinical studies with lenvatinib, events of posterior reversible encephalopathy syndrome (PRES) were reported in less than 1% of lenvatinib-treated subjects. PRES is a neurological disorder that can present with headache, seizure, lethargy, confusion, altered mental function, blindness, and other visual or neurological disturbances. Mild to severe hypertension may be present. MRI is necessary to confirm the diagnosis of PRES. Appropriate measures should be taken to control BP. In subjects with signs or symptoms of PRES, dose interruptions, reductions, or discontinuation may be required per instructions included in [Table 1](#). Please refer to Section 7 of the Investigator's Brochure for further information on lenvatinib, including the full set of special warnings and precautions for use (Section 7.4.4).

#### 9.4.1.2 Subsequent Treatment of Physician Choice (TPC)

The Subsequent Treatment Period (TPC period, Treatment Period 2) will begin upon the completion of lenvatinib Off-Treatment Visit in first-line treatment of lenvatinib. Subjects will be treated by commercially available, systemic TPC for uHCC. The first treatment of a single agent or combination of multiple drugs after lenvatinib treatment will be considered as the subsequent TPC. Locoregional therapies (ie, chemoembolization/radioembolization, etc.) will not be considered as a second line treatment following lenvatinib. If the investigator deems a subject inappropriate for commercially available systemic TPC as the subsequent treatment following lenvatinib, subjects will be followed in the survival Follow-Up Period.

All treatment following lenvatinib will be captured in the case report form. Data will be collected from the start of TPC, then at intervals as indicated in Schedule of Procedures/Assessments ([Table 3](#)).

Subjects starting subsequent systemic TPC  $\geq$ 8 weeks after lenvatinib off-treatment visit may be considered after discussion with sponsor.

For subjects who experience TPC-related toxicity, dose reduction and/or interruption will be in accordance with the prescribing information for each medication.

Subjects will continue to receive TPC treatment until disease progression, development of unacceptable toxicity, subject request, withdrawal of consent, or study termination by the sponsor.

#### 9.4.2 Identity of Investigational Product

[figure not shown]
The test drug (lenvatinib) in Treatment Period 1 will be supplied to the study sites by the sponsor packaged as open-label #4-size hydroxypropyl methylcellulose 4-mg capsules (yellowish-red cap and body, containing 4 mg lenvatinib [anhydrous free base]) in labeled containers.

Commercially available treatment chosen by investigator (TPC) for subsequent treatment of uHCC will be supplied by the local pharmacy.

Labelling, packaging and storage of the commercially available TPC must be in accordance with local regulations and manufacturer's instructions.

##### 9.4.2.1 Chemical Name, Structural Formula of E7080 (Lenvatinib)

- Test drug code: E7080
- Generic name: Lenvatinib
- Chemical name: 4-[3-Chloro-4-(*N*o-cyclopropylureido)phenoxy]-7-methoxyquinoline-6-carboxamide methanesulfonate
- Molecular formula: C21H19ClN4O4•CH4O3S
- Molecular weight: 522.96
- Structural formula:

##### 9.4.2.2 Comparator Drug

Not applicable

#### 9.4.2.3 Labeling for Study Drug

Lenvatinib will be labeled in accordance with text that is in full regulatory compliance with each participating country and is translated into the required language for each of those countries.

Medications chosen by investigator for subsequent treatment will not be provided by the sponsor.

#### 9.4.2.4 Storage Conditions

The sponsor will prepare the “Procedures for Handling Investigational Drug” which will be provided to the investigator, head of medical institution (as required by regional authority), or designated study drug manager before the investigational drug is delivered. The investigational drug will be stored in accordance with the “Procedures for Handling Investigational Drug.”

Lenvatinib will be stored in accordance with the labeled storage conditions. The expiry date for lenvatinib will be established based on the date that manufacturing/packing is completed or will be based on formulation testing, and will therefore be described in the “Procedures for Handling Investigational Drug.”

Study drug to be used in Period 2 will be stored as described in the locally approved product label or in the applicable Summary of Product Characteristics.

Temperature monitoring is required at the storage location to ensure that the study drug is maintained within an established temperature range. The investigator or designee (or if regionally required, the head of the medical institution) is responsible for ensuring that the temperature is monitored throughout the total duration of the study and that records are maintained. The temperature should be monitored continuously by using either an in-house validated data acquisition system, a mechanical recording device, such as a calibrated chart recorder, or by manual means, such that minimum and maximum thermometric values over a specific time period can be recorded and retrieved as required.

#### 9.4.3 Method of Assigning Subjects to Treatment Groups

This is an open-label, single-arm study. All subjects who provide signed informed consent to participate in this study and satisfy all eligibility requirements (see [Section 9.3](#)) will be assigned to receive lenvatinib treatment in Treatment Period 1 followed by the TPC in Treatment Period 2. There is no randomization in this study.

